17.8.2 Incomplete Stop Date

The following rules will be applied to impute the missing numeric fields for an incomplete prior or concomitant medication stop date. If the imputed stop date is before the start date (imputed or non-imputed start date), the imputed stop date will be equal to the start date.

Missing month and day

• If the year of the incomplete stop date is the same as the year of the last dose of study treatment, the month and day of the study exit date will be assigned to the missing fields

- If the year of the incomplete stop date is before the year of the last dose of study treatment, *December 31* will be assigned to the missing fields
- If the year of the incomplete stop date is after the year of the last dose of study treatment, *January 1* will be assigned to the missing fields

Missing month only

• If only the month is missing, the day will be treated as missing and both the month and the day will be replaced according to the above procedure

Missing day only

- If the month and year of the incomplete stop date are the same as the month and year of the last dose of study treatment, the day of the study exit will be assigned to the missing day
- If either the year of the incomplete stop date is before the year of the date of the last dose of study treatment or if both years are the same but the month of the incomplete stop date is before the month of the date of the last dose of study treatment, the last day of the month will be assigned to the missing day
- If either the year of the incomplete stop date is after the year of the date of the last dose of study treatment or if both years are the same but the month of the incomplete stop date is after the month of the date of the last dose of study treatment, the first day of the month will be assigned to the missing day

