9.0 PRIOR OR CONCOMITANT MEDICATION

Prior medication is defined as any medication taken before the date of the first IP insertion. *Concomitant medication* is defined as any medication taken on or after the date of first IP insertion. The WHO drug dictionary, version 2015 quarter 4 or newer, will be used to classify prior and concomitant medications by therapeutic class and drug name.

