17.8 MISSING DATE INFORMATION FOR PRIOR OR CONCOMITANT MEDICATIONS

For prior or concomitant medications, including rescue medications, incomplete (i.e., partly missing) start dates and/or stop dates will be imputed. When the start date and the stop date are both incomplete for a patient, the start date will be imputed first.

17.8.1Incomplete Start Date

The following rules will be applied to impute the missing numeric fields for an incomplete prior or concomitant medication start date. If the stop date is complete (or imputed) and the imputed start date is after the stop date, the start date will be imputed using the stop date.

Missing month and day

- If the year of the incomplete start date is the same as the year of the first dose of study treatment, the month and day of the first dose of study treatment will be assigned to the missing fields
- If the year of the incomplete start date is before the year of the first dose of study treatment, *December 31* will be assigned to the missing fields
- If the year of the incomplete start date is after the year of the first dose of study treatment, *January 1* will be assigned to the missing fields

Missing month only

• If only the month is missing, the day will be treated as missing and both the month and the day will be replaced according to the above procedure

Missing day only

- If the month and year of the incomplete start date are the same as the month and year of the first dose of study treatment, the day of the first dose of study treatment will be assigned to the missing day
- If either the year of the incomplete start date is before the year of the date of the first dose of study treatment or if both years are the same but the month of the incomplete start date is before the month of the date of the first dose of study treatment, the last day of the month will be assigned to the missing day.
- If either the year of the incomplete start date is after the year of the date of the first dose of study treatment or if both years are the same but the month of the incomplete start date is after the month of the date of the first dose of study treatment, the first day of the month will be assigned to the missing day

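### SAP 17.8.2 tests partial medication stop dates against the last dose but fills them in from study exit, so some year-only stop dates land before first insertion

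*SAP*

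**What the plan says.** SAP 17.8 sets the scope: "For prior or concomitant medications, including rescue medications, incomplete (i.e., partly missing) start dates and/or stop dates will be imputed". If both dates are partial, the start is imputed first.

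SAP 17.8.2 then handles partial stop dates.

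- **Month and day missing.** The condition is "If the year of the incomplete stop date is the same as the year of the last dose of study treatment", and the action is "the month and day of the study exit date will be assigned to the missing fields". A stop year before the last-dose year gets December 31; a later one gets January 1. A missing month alone is treated the same way.
- **Day missing.** If the month and year match those of the last dose, "the day of the study exit will be assigned to the missing day". An earlier month gets its last day; a later month gets its first.
- **Guard.** If the result precedes the start date, "the imputed stop date will be equal to the start date".

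For a partial start date in the first-dose year with month and day missing, SAP 17.8.1 says "the month and day of the first dose of study treatment will be assigned to the missing fields".

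SAP 9.0 calls a drug concomitant if it is "any medication taken on or after the date of first IP insertion", and prior if taken before that date. The SAP text available does not say whether the last dose means the last insertion or the last removal; SAP 17.4, on a missing last-dose date, is marked not applicable.

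**The concern.** The rule tests one date and borrows from another. The recorded year is kept, the exit month and day are attached to it, and nothing checks that exit fell in that year. If exit is in the next calendar year, the result is an early-year date in a year when the patient was treated much later.

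Prior or concomitant status under SAP 9.0 depends only on dates relative to first insertion. A drug that ran on through treatment can therefore be recorded as finished before treatment began. At stake is the accuracy of the concomitant-medication tables in SAP 9.1 and 9.2, including the table of pain medication identified from the concomitant-medication eCRF.

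The result also runs against the SAP's own convention. A stop of 2016 becomes 31 December 2016 if the last dose was in January 2017. It can become March 2016 if the last dose was in October 2016.

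**Working it through.** **1. Timeline, checked against the stated durations (Protocol 3 and 5.6; SAP 5.0).**

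- Treatment 1 only: 4 + 4 + 20 = 28 weeks, as stated.
- Treatment 2 maximum: 4 + 4 + 20 + 2 (rescheduling) + 2 + 4 = 36 weeks, as stated.

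In days from first insertion:

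| Course | Last insertion | Last removal | Exit |
|---|---|---|---|
| Treatment 1 only | 14 | 28 | 28 + 140 = 168 |
| Treatment 2 at Week 4 | 28 + 28 = 56 | 70 | 98 |
| Treatment 2 at Week 20, delayed 14 days | 168 + 14 = 182 | 196 | 224 |

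**2. How often exit falls in the year after the last dose.** With insertions spread evenly over the year, the share is (last dose to exit)/365.

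- Treatment 1 only: 140/365 = 38% if last dose means removal; 154/365 = 42% if it means insertion.
- Treatment 2: 28/365 = 8% or 42/365 = 12%.

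A day-by-day count over four calendar years gave 38.3%, 42.2%, 7.7% and 11.5%.

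**3. Where the year-only stop date lands.** It is the exit date moved back one year, so it precedes first insertion by 365 minus (first insertion to exit), plus one day when a leap day intervenes.

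- Treatment 1 only: 365 - 168 = 197 (197-198).
- Treatment 2 at Week 4: 365 - 98 = 267 (267-268).
- Treatment 2 at Week 20, delayed: 365 - 224 = 141 (141-142).

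In the four-year count it preceded first insertion in every cross-year case, except that an exit on 29 February gives no valid date in the year before.

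**4. Worked example with the guard.** First insertion 1 Oct 2016, second 15 Oct, removal 29 Oct, exit 18 Mar 2017, stop recorded as 2016. The rule gives 18 Mar 2016.

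| Start date | Stop after guard | Days before first insertion | Class |
|---|---|---|---|
| 2010, or 1 Feb 2016 | 18 Mar 2016 | 197 | prior only |
| 1 May 2016 | 1 May 2016 | 153 | prior only |
| 20 Jul 2016 | 20 Jul 2016 | 73 | prior only |
| 1 Oct 2016 | 1 Oct 2016 | 0 | concomitant |
| 5 Nov 2016 | 5 Nov 2016 | after insertion | concomitant |

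A start known only as 2016 is first set to 1 Oct 2016, so that drug also stays concomitant. SAP 17.8.1 has a clause that moves an imputed start back to an imputed stop. Because the start is imputed first, I read the 17.8.2 guard as the one that acts.

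**5. Missing day only.** The recorded month is kept and the day comes from the exit month.

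- Impossible date: last insertion 28 Feb 2016 + 154 days = exit 31 Jul 2016, so a stop of Feb 2016 becomes 31 February.
- Misplaced date: insertions on 15 and 29 Oct 2016 and exit on 1 Apr 2017 turn a stop of Oct 2016 into 1 Oct, 14 days before first insertion (last dose taken as insertion).
- Bound, on schedule and with last dose taken as insertion: the stop precedes first insertion only if both Treatment 1 insertions share a month, so first insertion is no later than the 31 - 14 = 17th and the error is at most 17 - 1 = 16 days. With Treatment 2 the last insertion is at least 56 days after the first, so this cannot happen.

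**The case against.** The strongest reply is that the fault is real but narrow. Most of that stands.

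A reader might infer any of the following, and the documents support none of them:

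- **Any drug with a year-only stop date is dated months before treatment.** The guard keeps drugs started on or after first insertion concomitant, along with those whose start is imputed to first insertion.
- **Collapsed durations distort the results.** The guard can shorten a record to one day, but SAP 9.1 and 9.2 tabulate patients and frequencies. No visible output uses time from start to stop.
- **Rescue use is misreported.** The rule formally covers rescue medication. Protocol 6.5.18, however, has IC pain medication logged electronically with date and time, and site staff fill gaps. The count of days on rescue medication in SAP 9.1 concerns medication recorded in that diary. Nothing shows that year-only dates arise there; eCRF entries are the likelier source.
- **Up to 42% of records are wrong.** That figure is a share of Treatment 1-only completers whose exit crosses a year end, not of medication records.
- **The missing-day rule is equally harmful.** Its error stays within one month, and the year-end shares do not apply to it.

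It can also be argued that year-only stop dates may belong mostly to pre-study history, since Protocol 6.5.18 collects medication details at every visit. For a drug that truly ended before insertion, prior is the right class, and a later imputed date would make it concomitant. This is a genuine trade-off. It does not defend the present rule, which reaches the prior class only by accident of when the patient exits, while the SAP already chooses the latest possible date for earlier years and months.

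**Conclusion.** The concern holds in limited form. SAP 17.8.2 mixes two reference dates, and nothing visible elsewhere in the SAP corrects it.

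For patients whose exit falls in the year after the last dose, a year-only stop date in the last-dose year precedes first insertion by about 197 days (Treatment 1-only completers) or about 141-268 days (Treatment 2). Drugs started before first insertion that in fact continued past it are then classed as prior only. The missing-day rule gives an arbitrary and sometimes impossible day, with an error confined to one month.

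The patient shares, 38-42% and 8-12%, assume even enrolment over the calendar year and completion on schedule. Each range reflects whether the last dose is the removal or the insertion. Year-end crossing is realistic: the protocol dates from January 2015, and Amendment 2 of April 2016 was written to speed enrolment. The number of partial stop dates is not given, so the number of misclassified records cannot be estimated.

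The primary ANCOVA in SAP 11.1 has no medication term and is unaffected. This is a minor correction to descriptive tables.

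**What to change.** In SAP 17.8.2, key both conditions to the study exit date:

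- If the partial stop date is in the exit year (month and day missing) or in the exit month and year (day missing), use the exit date.
- If it is in an earlier year or month, use December 31 of that year or the last day of that month.
- Never impute a date after exit.

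In the worked example the stop becomes 31 Dec 2016 and the drug counts as concomitant. Where exit is in the same year as the last dose, a year-only stop in that year is unchanged: first insertion 1 Mar 2016 and exit 16 Aug 2016 give 16 Aug 2016 under both rules. Impossible dates disappear.

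The cost is two lines of SAP text and the matching code, best made before database lock. The downside is that a drug truly stopped before insertion may be counted as concomitant. That matches the late-date convention the SAP already applies to stop dates before the last-dose year or month.

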17.9 CHARACTER VALUES OF CLINICAL LABORATORY PARAMETERS

If the reported value of a clinical laboratory parameter cannot be used in a statistical summary table because, for example, a character string is reported for a parameter of the numeric type, a coded value must be appropriately determined for use in the statistical analyses. The actual values, however, as reported in the database will be presented in the data listings.

Table 17.9–1 shows examples of how some possible laboratory results should be coded for the analysis.

Table 17.9–1.Examples of Coding Special Character Values for Clinical Laboratory
Parameters

| Laboratory Test, SI Unit | Possible Laboratory Results Coded Value for Analysis | | |
|-----------------------------|--|----------|--|
| CHEMISTRY | | | |
| ALT, U/L | < 5 | 5 | |
| AST, U/L | < 5 | 5 | |
| Bilirubin, total, µmol/L | < 2 | 2 | |
| URINALYSIS | | | |
| Chasses mms1/I | $= OR > 55, \ge 55, > 0$ | Positive | |
| Glucose, mmol/L | \leq 0, negative | Negative | |
| all | $> 8.0, \ge 8.0$ | 8.0 | |
| рн | ≥ 8.5 | 8.5 | |
| Ductoin | $= OR > 3.0, \ge 3.0, > 0$ | Positive | |
| Protein | ≤ 0 | Negative | |

ALT = alanine aminotransferase; AST = aspartate aminotransferase; SI = *Le Système International d'Unités* (International System of Units).

